### **2.3 Safety end-point**

- Incidence and frequency of Treatment-emergent adverse events (TEAEs), assessed throughout the study

### 3 CLINICAL SUPPLIES

#### 3.1 Treatment

##### 3.1.1 Description of products

The analytical certificates will be enclosed with the investigational medicinal product (IMP).

##### Test product

TEST PRODUCT	
IMP	Recombinant human Nerve Growth Factor (rhNGF), containing L-methionine as excipient 
 
- 20 µg/mL vials (Group 1),
 
- Vehicle vials (Group 2)
 

Manufacturer active substance	Dompé farmaceutici S.p.A., Italy
Manufacturer finished product	Bulk drug product manufactured by Patheon Italia S.p.A-Italy; Packaging and labelling performed by MontereSearch s.r.l. Italy
Pharmaceutical form	sterile buffered aqueous solution
Dose	6 times per day for 8 weeks
Administration route	Ophthalmic

##### 3.1.2 Dose regimen

The maximum dosing scheme of the different study groups is summarized in the following table:

Group	Doses to be tested	Dose (µg / day / eye)	Total daily dose (µg)/ both eyes	Total dose (µg)/both eyes in 56 days
Group 1	20 µg/mL (a)	4.80 µg	9.60 µg	537.6 µg
Group 2	Not Applicable	Not Applicable	Not Applicable	Not Applicable

(a) 1 drop/eye=40 µL

##### 3.1.3 Route and method of administration

Administration route and dose regimen for Groups 1 and 2 will be as follows:

**Group 1:** *rhNGF 20 µg/mL*: One drop (40 µL) corresponding to 0.80 µg of rhNGF will be instilled into each eligible eye six (both eyes, if applicable) times a day (every 2h), for a total daily dose of 9.6 µg (both eyes, if applicable), for 56 consecutive days. Total dose will be 537.6 µg/56 days if both eyes are treated.

**Group 2:** *Vehicle*: One drop (40 µL) will be instilled into each eligible eye (both eyes, if applicable) six times a day (every 2h).

Enrolled patients will self-administer the eye drops at home into both eyes unless only one eye meets the eligibility criteria (in both group 1 and 2).

The Investigator will check that all patients take the IMP appropriately verifying the diary and the used and/or unused medication returned.

### 3.2 Packaging, labelling, distribution and storage

#### 3.2.1 Formulation and packaging

The Investigator will be provided with frozen IMP solutions ( $-20 \pm 5^{\circ}\text{C}$ ) containing rhNGF at 20 µg/mL (for the dosing Group 1) and vehicle (for group 2) in one monthly box containing 4 weekly boxes.

One monthly box including four weekly boxes containing the treatments for each day will be delivered to the patient at each study visit according to the following scheme:

**Table 3.2.1.1 Investigational Medicinal Product delivery plan**

Box delivery	Boxes to be provided
Day 0	Week 1, Week 2, Week 3, Week 4 (Day 0 - Day $28 \pm 2$ ) - 1 Box rhNGF/Vehicle
Day $28 \pm 2$	Week 5, Week 6, Week 7, Week 8 (Day 29 - Day $56 \pm 2$ ) - 1 Box rhNGF/Vehicle

Each weekly box will contain a total of 7 vials of rhNGF (Group 1) or Vehicle (Group 2).

#### 3.2.2 Labelling, Storage and handling

##### Labelling

The medication labelling will report all the information requested according to the Annex 13 to the Good Manufacturing Practice (published by the Commission in The rules governing medicinal products in the European Community, Volume 4) as follows:

- a. Name, address and telephone number of the Sponsor, contract research organisation or Investigator (the main contact for information on the product, clinical study)
- b. Pharmaceutical dosage form, route of administration, quantity of dosage units, and in the case of open studies, the name and strength
- c. The batch code number to identify the contents and packaging operation

- d. A study reference code allowing identification of the study, site, Investigator and Sponsor if not given elsewhere
- e. The study patient identification study number and where relevant, the treatment period
- f. Directions for use (reference may be made to a leaflet or other explanatory document intended for the study patient or person administering the product)
- g. “For clinical study use only” or similar wording
- h. The storage conditions
- i. Period of use (use-by date, expiry date or re-test date as applicable), in month/year format and in a manner that avoids any ambiguity
- j. “Keep out of reach of children”

Labels will be in local language.

### **3.2.3 Storage and handling**

The Pharmacist and/or Investigator will be responsible for receipt, proper storage and usage of study drug.

The investigational product must be stored at  $-20 \pm 5$  °C at the Investigational sites, in an appropriate locked room accessible only to the pharmacist, the Investigator or a duly designated person.

A temperature probe and data logger will accompany the drug on shipment. It is essential that the Investigational sites will verify the temperature excursion during shipment vs. the acceptable storage conditions, in order to identify potential stability concerns during shipment. These must be immediately communicated to the Sponsor that will decide upon appropriate actions to be taken. The IMP will be stored in a locked place, sheltered from light. The vials will be not shaken since agitation of vials may cause foaming and/or particle formation.

On Day 0 and at Week 4 visits the patients will receive from the study personnel 4 weekly boxes containing the study medications in a refrigerated bag. The refrigerated bag will be used to ensure that the medications will maintain refrigeration temperatures during transport to the patient’s home.

Patient should bring the study medication, one monthly box containing 4 weekly kits, at home as soon as possible and immediately store it in a freezer at  $-20 \pm 5$  °C.

The weekly kit in use must be kept at 2-8°C for 7 days, the daily vial can be kept at room temperature before the patient will use the single vial for each instillation (both eye) as far as 12 hours are not exceeded.

Together with the IMP weekly box, the patients will be provided with a sufficient number of syringes and adaptors to be used for the administration of the IMP for the following 4 weeks. Syringes and adaptors will be provided separately in single sterile PE packages and may be kept at room temperature.

The syringe is used with an adaptor consisting of a connecting device with dual connections: one end for the syringe and one end for the vial. Patients will need to:

- 1) put the adaptor on the top of the vial (after removing the plastic seal) by piercing the septum
- 2) put the syringe on adaptor inlet
- 3) draw the solution contained in the vial with the syringe until this reaches its predetermined capacity
- 4) remove the syringe and use it as a dropper to administer one drop of IMP into each eye
- 5) the syringe must be discharged after each administration to both eyes, if applicable

### **3.3 Drug accountability**

After receipt of the IMP supply, the pharmacist and/or Investigator will confirm in writing by signing and dating standard drug accountability forms.

Every four weeks from the start of the treatment the patients will return the used or unused study boxes to the Investigator.

The Pharmacist and/or Investigator, who will keep a cumulative inventory and dispensing records, will maintain all supplies under adequate security.

The Investigator will maintain an accurate record about the shipment and dispensing of the test drug, using a drug accountability ledger. An accurate drug disposition record will be kept specifying the date and amount dispensed to each patients.

Adequate record of receipt, use, return or loss of drug will be retained. This inventory record must be available for inspection by the Sponsor and regulatory inspection at any time. Copies of this record will be provided to the Sponsor by the CRO at the conclusion of the study.

At each scheduled visit the diary should be reviewed with the patient for completeness. Missing information should not be provided during the diary check but reported as missing

Partially used or unused study drug boxes will be returned to the Sponsor, at the end of the study.

At the conclusion of the study, and if appropriate during the course of the study, the Investigator will complete the drug accountability forms. Within one month after completion of the trial the unused study medication will be shipped to the Sponsor or will be destroyed after authorisation by the Sponsor by an authorised company according to GCP regulations.

## **4 INVESTIGATIONAL PLAN**

### **4.1 Overall study design**

This is a Phase II study, single-centre, randomized, double masked, parallel arm, vehicle-controlled trial.

Randomization will be 2:1 of 180 post cataract or refractive surgery patients to rhNGF eye drops solution at 20 µg/ml (120 patients) or vehicle eye drops solution (60 patients) 6 times per day for 8 weeks.

The patients will be involved in the study for a maximum of 12 weeks from Day 0 visit to Week 12 follow-up visit.

### **4.2 Discussion of design**

The proposed phase II study is a single-centre, randomized, double masked, parallel arm, vehicle-controlled trial, designed to evaluate the preliminary efficacy and safety of rhNGF eye drops at 20 µg/ml concentration administered six times daily for 8 weeks in patients' eyes who underwent cataract and corneal refractive surgery, both known to damage the corneal sensory nerve plexus.

Patients will be evaluated at baseline (day 0), week 4 (28±2 days), week 8 (day 56±2) or early exit and 4 weeks (day 84±2) after the end of study treatment.

## **5 STUDY POPULATION**

### **5.1 Target population**

Male and female patients  $\geq 18$  years old, who had undergone post cataract and refractive surgery.

### **5.2 Inclusion criteria**

To be enrolled in this study, patients must fulfil all these criteria:

1. Male or female  $\geq 18$  years old
2. Patients who are characterized by the following clinical features:
  - a. History of cataract or refractive corneal surgery in the study eye(s) in the previous 6 months;
  - b. Mean Symptom Assessment in Dry Eye (SANDE) score for severity and frequency of at least 30 at baseline
3. The same eye (study eye) must fulfill all the above criteria
4. Best corrected distance visual acuity (BCDVA) score of  $\geq 0.1$  decimal units in both eyes at the time of study enrolment
5. Female patients must have negative pregnancy urine test if at childbirth potential.
6. Only patients who satisfy all requirements for informed consent may be included in the study. Written Informed Consent must be obtained before the initiation of any study-specific procedures.
7. Patients must have the ability and willingness to comply with study procedures.

### **5.3 Exclusion criteria**

Patients meeting any of these criteria will not be enrolled in the study:

1. Any ocular disease other than Dry Eye requiring treatment with topical medications in either eye at the time of study enrolment.
2. Any active ocular infection or active inflammation in either eye unrelated to Dry Eye.
3. Presence or history of any systemic or ocular disorder, condition or disease (with particular attention to malignancies and neuro-oncological diseases) that could possibly interfere with the conduct of the required study procedures or the interpretation of the study results.
4. Use of therapeutic or Refractive Contact lenses in either eye at the time of study enrolment;
5. History of ocular surgery in the study eye(s), excluding corneal refractive or cataract procedures, within 90 days of study enrolment.
6. Females of childbearing potential (those who are not surgically sterilized or post-menopausal for at least 1 year) are excluded from participation in the study if they meet any one of the following conditions:
  - a. are currently pregnant or,
  - b. have a positive result at the urine pregnancy test (Baseline/Day 0) or,
  - c. intend to become pregnant during the study treatment period or,
  - d. are breast-feeding or,

- e. are not willing to use highly effective birth control measures, such as: hormonal contraceptives - oral, implanted, transdermal, or injected - and/or mechanical barrier methods - spermicide in conjunction with a barrier such as a condom or diaphragm or IUD - during the entire course of and 30 days after the study treatment periods.
7. Participation in another clinical study at the same time as the present and within 30 days of study enrolment;
8. History of drug, medication or alcohol abuse or addiction.

### **5.3.1 History of drug, medication or alcohol abuse or addiction. Allowed/Disallowed treatments**

All medications (including over-the-counter drugs, herbal products, vitamins, and antacids) taken within 4 weeks prior to the start of and throughout the study must be recorded on the case report form. Medication entries should be specific to product name (if a combination drug product) and spelled correctly. The dose, unit, frequency, route of administration, start date, discontinuation date, and indication should also be recorded. For medications administered only one time, the frequency column may reflect "once".

Any systemic or topical ocular treatment is allowed, as prescribed by the treating physician both during treatment and follow-up periods.

## **6 STUDY SCHEDULE**

The schedule of the study is summarized at the end of the synopsis (page 9).

### **6.1 Study visits and procedures**

Each enrolled patient will undergo 4 visits.

Maximum study duration will be 12 weeks, Baseline/Day 0 visit included. A written informed consent will be obtained before any study assessment or procedure.

The first patient first visit (FSFV) is defined as the 1st visit performed at the clinical centre by the 1st screened patient. The last patient last visit (LSLV) is defined as the last visit performed at the clinical centre (or the telephonic follow-up, if applicable) by the last patient, i.e. the last visit foreseen by the study protocol, independently of the fact that the patient is a completer or a withdrawn patient.

The following phases, visits and procedures will be performed:

#### **➤ Interventional phase**

- Baseline/Day 0 Visit - Day 0
- Week 4 Visit - Day 28 ± 2
- Week 8 Visit - Day 56 ± 2/Early Termination Visit (ETV). In case of study discontinuation patients will undergo the assessments foreseen at Week 8 visit.

#### **➤ Follow-up phase**

- Week 12 Visit Follow-Up - Day 84 ± 2

	Day	Procedures/Assessments
Baseline Visit	Day 0	
 
➤ Explanation to the patient of study aims, procedures and possible risks
 
➤ Informed consent signature
 
➤ Screening number allocation (as S001, S002, etc.)
 
➤ Demographic data
 
➤ Medical and surgical history/current medical conditions
 
➤ Prior/concomitant medications
 
➤ AE monitoring
 
➤ Ocular examination of both eyes:               
 
1. Assessment by Symptom Assessment iN Dry Eye (SANDE)
 
2. Assessment of best corrected distance visual acuity (BCDVA)
 
3. Slit lamp examination (SLE) to assess the Eyelid - Meibomian glands, Eyelid – Erythema, Eyelid - Oedema Lashes, Conjunctiva Erythema, Lens, Iris, Anterior Chamber
 
4. External Ocular Examination
 
5. Corneal Confocal Microscopy (Only for patients who underwent LASIK surgery)
 
 
Ten minutes break
 
6. Tear Film Break Up Time (TFBUT)               
Five minutes break
 
7. Corneal sensitivity (Cochet-Bonnet)               
Ten minutes break
 
8. Ocular surface staining (NEI score)               
Ten minutes break
 
 
➤ Frequency of patient's own artificial tear use (to be reported in eCRF)
 
➤ Pregnancy test for female patients.
 
➤ Patient eligibility: Inclusion/exclusion criteria evaluation
 
➤ Assignment of study eye(s) (Note: if both eyes are eligible, study treatment will be administered to both eyes, and each eye will be considered as "study eye")
 
➤ Randomization
 
➤ Study Drug Dispensation
 

 
Note: At the study visit the Investigator will provide each patient with diary and one monthly box of the study drug for the following 4 weeks together with an adequate number of adaptors and syringes.
 
After visit completion patients will start topical ocular treatment as per instructions and will self-administer at home the IMP. Patients will return to the clinical site on Day 28 ± 2 (Week 4 Visit).
 
The patients will be instructed to fill in the diary with time of self-administration, potential AE occurrence, concomitant medication intake and the quantity of artificial tears used, and to return the refrigerated box on the Week 4 visit.

At home	Days 0-28±2	
 
➤ Self-administration at home of the IMP, six times daily every 2 h in every study eye (diary)
 
➤ Artificial tears use (diary)
 
➤ Recording any new or changes in concomitant medications (diary)
 
➤ Recording any unusual medical conditions - AE monitoring (diary)
 
 
Data will be recorded by the patient on the patient's diary.

	Day	Procedures/Assessments
Week 4 Visit	Day 28±2	
 
➤ Assessment of compliance to treatment (from patient diary and IMP reconciliation from returned weekly boxes)
 
➤ Current medical conditions
 
➤ Concomitant medications
 
➤ AE monitoring
 
➤ Ocular examination of both eyes:               
 
1. Assessment by Symptom Assessment iN Dry Eye (SANDE)
 
2. Slit lamp examination (SLE) to assess the Eyelid - Meibomian glands, Eyelid – Erythema, Eyelid - Oedema Lashes, Conjunctiva Erythema, Lens, Iris, Anterior Chamber
 
3. External Ocular Examination
 
 
Ten minutes break
 
 
4. Tear Film Break Up Time (TFBUT)
 
 
Ten minutes break
 
 
5. Ocular surface staining (NEI score)
 
 
Ten minutes break
 
 
➤ Frequency of patient’s own artificial tear use (to be reported in eCRF)
 
➤ Pregnancy test for female patients.
 
➤ Study Drug Dispensation
 
 
Note: At the study visit the Investigator will provide each patient with diary and one monthly box of the study drug for the following 4 weeks together with an adequate number of adaptors and syringes.
 
After visit completion the patients will continue study treatment as per instructions and will self-administer at home the IMP. Patients will return to the clinical site on Day 56 ± 2 (Week 8 Visit).
 
The patients will be instructed to fill in the diary with time of self-administration, potential AE occurrence, concomitant medication intake and the quantity of artificial tears used.

At home	Days 28±2 -56±2	
 
➤ Self-administration at home of the IMP, six times daily every 2 h (diary) in every study eye
 
➤ Artificial tears use (diary)
 
➤ Recording any new or changes in concomitant medications (diary)
 
➤ Recording any unusual medical conditions - AE monitoring (diary)
 
 
Data will be recorded by the patient on the patient’s diary.

	Day	Procedures/Assessments
Week 8 Visit	Day 56±2  Or  Early termination (if applicable)	
In case of study early discontinuation (at any time) patients will undergo the assessments foreseen at Week 8 visit.
 
 
➤ Compliance to treatment (from patient diary and control of returned weekly boxes)
 
➤ current medical conditions
 
➤ concomitant medications
 
➤ AE monitoring
 
➤ Ocular examination in both eyes:               
 
1. Assessment by Symptom Assessment iN Dry Eye (SANDE)
 
2. Assessment of best corrected distance visual acuity (BCDVA)
 
3. Slit lamp examination (SLE) to assess the Eyelid - Meibomian glands, Eyelid – Erythema, Eyelid - Oedema Lashes, Conjunctiva Erythema, Lens, Iris, Anterior Chamber
 
4. External Ocular Examination
 
5. Corneal Confocal Microscopy (Only for patients who underwent LASIK surgery)
 
 
Ten minutes break
 
6. Tear Film Break Up Time (TFBUT)
 
Five minutes break
 
7. Corneal sensitivity (Cochet-Bonnet)
 
Ten minutes break
 
8. Ocular surface staining (NEI score)
 
Ten minutes break
 
 
➤ Frequency of patient’s own artificial tear use (to be reported in eCRF)
 
➤ Pregnancy test for female patients.
 
 
Note: The Investigator will deliver to the patients the diary. Patients will return to the clinical site on Day 84 ± 2 (Week 12 Visit). The patients will be instructed to fill in the diary with AE occurrence, concomitant medication intake and the quantity of artificial tears used.

At home	Days 56±2-84±2	
 
➤ Artificial tears use (diary)
 
➤ Recording any new or changes in concomitant medications (diary)
 
➤ Recording any unusual medical conditions - AE monitoring (diary)
 
 
Data will be recorded by the patient on the patient’s diary.

Week 12 Visit Follow-Up	Day 84±2	
 
➤ Current medical conditions
 
➤ Prior/concomitant medications
 
➤ AE monitoring
 
➤ Ocular examination in both eyes:               
 
1. Assessment by Symptom Assessment iN Dry Eye (SANDE)
 
2. Assessment of best corrected distance visual acuity (BCDVA)
 
3. Slit lamp examination (SLE) to assess the Eyelid - Meibomian glands, Eyelid – Erythema, Eyelid - Oedema Lashes, Conjunctiva Erythema, Lens, Iris, Anterior Chamber
 
4. External Ocular Examination
 
 
Ten minutes break
 
5. Tear Film Break Up Time (TFBUT)
 
Ten minutes break
 
6. Ocular surface staining (NEI score)
 
Ten minutes break
 
 
➤ Frequency of patient’s own artificial tear use (to be reported in eCRF)
 

## **7 DESCRIPTION OF SPECIFIC PROCEDURES**

### **7.1 Ophthalmological Evaluations**

Ocular evaluations will be performed on both eyes even if just one eye is eligible (determined as study eye). The assessments must always be performed according the sequence detailed in Par 6.1. The assessment will be performed at Day 0 Baseline Visit, Week 4 Visit, Week 8 Visit and at Week 12 Visit. The ophthalmological assessment will include:

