## Study Schedule

Study procedures	Baseline Visit (Day 0)	Week 4 (Day 28±2)	Week 8** (ETV) (Day 56±2)	Week 12 (Follow-up Visit) (Day 84±2)
Informed Consent	X			
Inclusion/Exclusion Criteria	X			
Urine Pregnancy Test	X	X	X	
Randomization	X			
Demographics	X			
Ocular and General Medical History	X			
Previous and Concomitant Ocular And Systemic Medications	X	X	X	X
Frequency of artificial tear use	X	X	X	X
Record Adverse Events (AEs)	X	X	X	X
Verify patient study medication dosing compliance		X	X	
SANDE questionnaire	X	X	X	X
Best Corrected Distance Visual Acuity (BCDVA)	X		X	X
Cochet-Bonnet aesthesiometry	X		X	
External Ocular Examination	X	X	X	X
Slit Lamp Examination (SLE)	X	X	X	X
Fluorescein staining (NEI scale)	X	X	X	X
Tear Film Break-up Time (TFBUT)	X	X	X	X
Corneal confocal microscopy*	X		X	
Study drug dispensation	X	X		

* Only for patients who underwent LASIK surgery            ** ETV – Early Termination Visit to be performed according to Visit Week 8 procedures, if premature treatment discontinuation occurs.            Note: Patient diary will be reviewed for potential AEs, and details as applicable            Abbreviations: SANDE - Symptom Assessment In Dry Eye
				

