### **7.1.6 Corneal sensitivity**

For the assessment of corneal sensation the Luneau Cochet-Bonnet aesthesiometer (Western Ophthalmics Corporation©) should be used.

The Cochet-Bonnet aesthesiometer contains a thin, retractable, nylon monofilament that extends up to 6 cm in length. Variable pressure can be applied to the cornea by adjusting the monofilament length. The monofilament length ranges from 6 to 0.5 cm. As the monofilament length is decreased the pressure increases from 11 mm/g to 200 mm/g.

Corneal sensation will be measured in both eyes in each of the four quadrants of the cornea using the Cochet Bonnet aesthesiometer before the instillation of any dilating or anesthetic eye drops.

Steps for using the Cochet Bonnet aesthesiometer: extend the filament of the aesthesiometer to full length of 6 cm. Slowly advance the monofilament towards the eye until the tip perpendicularly touches the corneal surface. Continue to exert a slight pressure until obtaining an inflection deviation of the filament of about 4% (i.e. the first visible inflection). If a positive reaction to the touch of cornea is elicited proceed to step 3. If a positive reaction is not achieved proceed to step 2. (NOTE: A positive response is any action indicating corneal sensation whether communicated verbally or physically).

Retract the filament incrementally in 0.5 cm and repeat this step until the patient gives a positive reaction indicating that the contact of the monofilament on the cornea has been sensed. (NOTE: The shorter filament lengths indicate decreased corneal sensation).

Record the length of the filament in cm at which the patient sensed the contact with the cornea.

Repeat steps 1-3 in each of the 4 corneal quadrants (superior nasal, inferior nasal, superior, temporal and inferior temporal) in the study eye(s) and in each of the 4 corneal quadrants of the other eye (not the study eye, if applicable).

To clean the instrument, please refer to your national standards for devices that contact the eye and tears or follow the suggested manufacturer's recommendations.

The length of the filament in cm at which the patient corneal sensation was observed for the tested area of the cornea will be entered into the eCRF.

Corneal sensitivity findings will be entered in the eCRF.

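### Cochet-Bonnet filament contact precedes the co-primary corneal staining at Baseline and Week 8 but not at Weeks 4 and 12; any staining it leaves could differ by arm if rhNGF changes corneal sensation

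*Protocol*

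**What the plan says.** Protocol 7.1 makes the order in section 6.1 binding: "The assessments must always be performed according the sequence detailed in Par 6.1". In the 6.1 visit tables, Baseline and Week 8/early termination run TFBUT (step 6), a five-minute break, Cochet-Bonnet (step 7), a ten-minute break, then NEI staining (step 8). Weeks 4 and 12 run TFBUT, a ten-minute break, then NEI staining, without Cochet-Bonnet.

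The Study Schedule has the row "Cochet-Bonnet aesthesiometry" marked at Baseline and Week 8. It does not carry the LASIK-only footnote that confocal microscopy carries, so it applies to all patients.

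Protocol 7.1.6 describes a contact test: "Corneal sensation will be measured in both eyes in each of the four quadrants of the cornea". The tip is brought to the cornea and pressed until the filament just bends. It starts at 6 cm and is shortened by 0.5 cm after each touch that is not felt. "As the monofilament length is decreased the pressure increases from 11 mm/g to 200 mm/g".

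The co-primary endpoint (SAP 7.2.7) is the change from baseline to Week 8 in corneal staining in the Main Eye, scored 0 to 15 over five sectors. Corneal sensitivity is a secondary efficacy endpoint.

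**The concern.** Corneal staining grades surface damage, and at the two visits that define the co-primary endpoint it is read on a cornea that has just been touched. The amount of touching is not constant. An eye that feels the first touch in each quadrant gets few, light contacts; an eye with poor sensation gets more, with a stiffer filament.

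Sensation is something rhNGF is meant to improve: Protocol 1.3 gives repair of the damaged corneal nerve plexus as the potential benefit. If sensation recovers more on rhNGF than on vehicle, rhNGF eyes receive fewer and lighter touches at Week 8, and their staining could look better partly because of the test. Randomisation and masking do not prevent this, because the path runs through an effect of treatment that arises after randomisation. The sign endpoint and the sensation endpoint would then not be cleanly separate.

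The order also differs between visits, so the time course of staining mixes touched and untouched readings.

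**Working it through.** **Order and contacts before staining is graded (Protocol 6.1 and 7.1.6)**

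| Visit | Steps leading to staining | Filament contacts per eye |
|---|---|---|
| Baseline | TFBUT, 5 min, Cochet-Bonnet, 10 min, staining | 4 to 48 |
| Week 4 | TFBUT, 10 min, staining | 0 |
| Week 8/early termination | TFBUT, 5 min, Cochet-Bonnet, 10 min, staining | 4 to 48 |
| Week 12 | TFBUT, 10 min, staining | 0 |

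Filament lengths 6.0, 5.5, ..., 0.5 cm give 12 lengths, so 1 to 12 contacts per quadrant. Over four quadrants this is 4 × 1 = 4 to 4 × 12 = 48. In the protocol's units, pressure rises up to 200/11 = 18.2-fold. The upper ends require no response until the shortest filament in all four quadrants.

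**The plan's own sample size for the co-primary endpoint.** Inputs (Protocol 10.2, SAP 3.6): difference 1.0, SD 2.2, two-sided alpha 0.05, power 80%, allocation 2:1, 5% dropout.

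- Equal allocation: n = 2 × [2.2 × (1.960 + 0.842)/1.0]² = 75.98, so 76.
- 2:1: n1 = 0.5 × 76 × 3 = 114; n2 = 0.5 × 76 × 1.5 = 57.
- Dropout: 114/0.95 = 120; 57/0.95 = 60. Power at 114 versus 57 is 80.0%.

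The stated figures reproduce. This point does not dispute them.

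**What cancels and what does not.** Baseline precedes randomisation, so the expected baseline artefact is the same in both arms. The bias in the treatment comparison is therefore the between-arm difference in mean artefact at Week 8, called d. If d = 0, nothing remains.

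**Effect of an assumed d.** The documents give no value, so the range is illustrative. A d of 0.1 to 0.3 corresponds to a net one-step change in one sector in 10 to 30 of every 100 patients in one arm relative to the other.

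- SE = 2.2 × √(1/57 + 1/114) = 0.357.
- Two-sided rejection with no true effect = 1 − Φ(1.960 − d/SE) + Φ(−1.960 − d/SE).

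| d (points) | d/SE | Rejection |
|---|---|---|
| 0 | 0 | 5.0% |
| 0.1 | 0.28 | 5.9% |
| 0.2 | 0.56 | 8.7% |
| 0.3 | 0.84 | 13.4% |

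**LOCF route.** Suppose 5% of patients (the planned dropout) have an untouched Week 4 score carried forward, and assume an artefact of 0.5 to 2 points. An arm mean then shifts by 0.05 × 0.5 = 0.025 to 0.05 × 2 = 0.1 points. The treatment comparison is biased only to the extent that such values are more common, or the artefact larger, in one arm.

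**Weeks 4 and 12.** The change from baseline is an untouched score minus a touched one, so any baseline artefact adds to the apparent improvement in both arms. SAP 9.5.2 applies ANCOVA only at Week 8, so these results are descriptive.

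**The case against.** The strongest objection is that the key premise is not in the documents. Neither says that filament contact leaves staining that can be graded, or that a mark lasts ten minutes. Protocol 7.1.6 asks for slight pressure only, to the first visible bend, and the ten-minute break is a safeguard. This stands: the mechanism is a physical inference, and the point is conditional on it.

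Second, Baseline and Week 8 use the same order, so the main contrast compares like with like. This stands for any artefact equal in both arms. It does not dispose of one that follows a treatment effect on sensation. How large that could be is unknown: no inclusion criterion requires reduced sensation, and no baseline sensation data are given. If most eyes respond near 6 cm, exposure will hardly vary.

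Third, patients who stop early are to have the Week 8 procedures, including Cochet-Bonnet, so their last reading is normally a touched one. An untouched Week 4 score is carried forward mainly when no termination visit takes place or the Week 8 score is missing. A reader might infer that LOCF builds in a sizeable advantage; the plan does not support that.

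Fourth, the SAP (3.7 and 8.2.1.3) calls all inference exploratory. That limits the consequence of a false positive, but the trial was sized on this endpoint and the SAP tests it at 5%.

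**Conclusion.** The plan allows a contaminant of the co-primary endpoint that could depend on treatment, and grading staining first would avoid it. The order of steps, and the rise in contacts and pressure as sensation falls, are established from the text. Bias in the Week 8 comparison rests on two further assumptions: that contact leaves gradable staining beyond ten minutes, and that sensation at Week 8 differs by arm enough to change exposure. Under an assumed 0.1 to 0.3 point difference, false-positive risk would be 5.9% to 13.4% instead of 5.0%. The Week 4 and Week 12 effect is confined to descriptive results, and the LOCF route is minor.

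A reader might go further and infer that the co-primary result is invalid, or that 48 touches, an 18-fold pressure range and one sector raised by one grade describe the expected bias. They do not. The first two are theoretical limits. The third sets a single-eye score beside a between-arm mean difference: a bias of 1.0 point would need a net one-step artefact per patient, on average, in one arm and none in the other.

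**What to change.** In Protocol 6.1, at Baseline and Week 8/early termination, grade NEI staining after TFBUT with the ten-minute break used at Weeks 4 and 12, and perform Cochet-Bonnet after staining. Changing the order alone is not enough, because the break after TFBUT is now five minutes at Baseline and Week 8 and ten at the other visits.

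The new order breaks no stated rule. Fluorescein for TFBUT already precedes Cochet-Bonnet, and 7.1.6 bars only dilating and anaesthetic drops beforehand. The cost is an edit to two visit tables, with no added procedure and no change to the sample size of 180. The breaks from TFBUT onward now total 5 + 10 + 10 = 25 minutes. With ten minutes before staining and the existing ten minutes after it, they would total 20. The downside is that sensation is measured slightly later in the visit and after a second staining step.

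This does not make conditions uniform for LASIK patients. They would still have confocal microscopy, with anaesthetic drops and gel (Protocol 7.1.8), before staining at Baseline and Week 8 only. For those patients, 6.1 and 7.1.8 place anaesthetic drops before Cochet-Bonnet, whereas 7.1.6 requires Cochet-Bonnet before any such drops. These sections should be reconciled.
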